For this study, participants will be provided \$75 for screening and \$50 for each experimental session thereafter with an additional \$50 bonus earned for each experimental session for those who complete the study (up to 9 in-person laboratory experimental sessions including initial exposure sessions for a total \$450 in bonus payments). This payment system provides an approximately equivalent compensation rate per visit as provided in a previous long-term laboratory studies (IRB00107178). Due to the substantial time given by each participant over the course of roughly 2-3 weeks, participants will be able to earn up to \$975 for completing the study. Additionally, if a participant refers someone to the study who then completes the study, the referring participant will receive a one-time bonus payment of \$200. This referral bonus will be retroactively applied to any referring participant who has previously completed the study.

11. Costs

- a. Detail costs of study procedure(s) or drug (s) or substance(s) to participants and identify who will pay for them.

There will be no cost to study volunteers for participating in the study.

Date: February 18, 2023

Principal Investigator: [name].

Application Number: IRB00264306

NCT04595279

References

Hursh SR. Economic concepts for the analysis of behavior. *J Exp Anal Behav* 1980;34(2):219-238.

Hursh SR. Behavioral economics. *J Exp Anal Behav* 1984;42(3):435-452.

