Interested individuals will call the study contact number, and study personnel will conduct a brief screening for eligibility over the phone. To facilitate timely screening of participants for eligibility, website ads and flyers will contain a link to a brief online interest and eligibility survey using JHM Qualtrics. All individuals will be phone screened and, if qualified, scheduled for an in-person screening visit (approximately 2 hrs.) at the Behavioral Pharmacology Research Unit (BPRU) at the Johns Hopkins Bayview Medical Campus. Individuals will not sign consent before telephone screening. For those who meet phone screen eligibility, the laboratory screening will include physical and mental health history, drug history, physical examination, and standard laboratory tests of blood chemistry and hematology.

General Procedures: We will recruit and consent up to 100 individuals to accrue 35 non-treatment seeking male and female dependent cigarette smokers to complete the study by advertising and word-of-mouth. These volunteers will be medically healthy smokers without immediate intention to quit and will be fully informed community non-treatment seeking volunteers, who do not constitute a special vulnerable population. They will participate in a 9-session laboratory study at the Behavioral Pharmacology Research Unit at the Johns Hopkins Bayview Campus.

All lab visits will last approximately 4 hours total. Participants will be instructed to abstain from smoking for 6 hours before the beginning of each daily session in order to achieve a carbon monoxide (CO, a byproduct of smoking; measured by the Smokerlyzer, CoVita, Haddonfield, NJ, USA) measure $\leq 50\%$ of the CO value obtained at the initial screening. If a participant fails to meet this criterion, the session will be rescheduled (or participation discontinued after multiple such instances). Sessions will be conducted at various times throughout the day, but each

Date: February 18, 2023

Principal Investigator: [name].

Application Number: IRB00264306

NCT04595279

individual participant will always begin his or her sessions at the same time of day throughout the experiment.

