Greenwashing Manipulations (Sessions 1-9): During behavioral sessions participants will have the opportunity to smoke at least 1 of 2 types of cigarettes (topography sessions will involve the opportunity to smoke 1 type per session, whereas both types will be available during behavioral economic sessions and participants can choose to smoke either or both). Participants will be exposed to advertising for two different novel cigarette brands. One brand will be advertised using greenwashing tactics, while the other brand will have control advertising lacking the greenwashing tactics. To avoid a brand x greenwashing confound, the brand that is advertised with greenwashing materials will randomly vary across participants (e.g., Participant 1 may see Brand A advertised with greenwashing; Participant 2 may see Brand A advertised with the control ads). Participants will be exposed to the materials in two ways designed to replicate real world exposure to cigarette marketing for 30 minutes before sessions. First, posters will be placed on the walls to mimic advertising in retail settings. Participants will also be given printed information about each brand, designed to mimic direct mail advertisements, and may view this information as long as they like during the 30 minutes. These advertising materials and cigarette packs will remain in the room during topography and behavioral economic sessions. Unknown to the participants, both brands of cigarettes (Brand A and Brand B) will be the same commercial brand of cigarette. The study team will purchase cigarettes from a local store that sells commercially-available cigarettes. The study team will repackage these cigarettes into new packages that have either greenwashing elements or a control package that is similar, but without greenwashing elements. Although the two brand names and advertisements will be the same across participants, the actual commercial brand of cigarette used will be individualized for each participant to roughly the nicotine and menthol content for the participants typical brand of cigarettes. We will also ensure that it is a brand that lacks distinctive markings on the cigarettes that would allow for identification. Because this is within-subjects research that tests the effects of greenwashing, the brand used is arbitrary aside from the above considerations.

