Topography sessions (Sessions 1-2): After assuring ≥ 6 hours of smoking abstinence via breath CO requirements, participants will take part in a 3-hour smoking topography session. In one session participants will have the ability smoke cigarettes associated with the greenwashing techniques, and in the other session participants will have the ability to smoke control cigarettes without the greenwashing technique used in labelling. Order of the two sessions will be randomized and counterbalanced across participants. Participants will be free to smoke cigarettes ad lib and in any manner they choose (e.g., depth and timing of inhalations) so long as they smoke the cigarettes through the small cigarette holder connected to our existing topography equipment (currently in use for IRB00107178). From this 3-hour session, topography measures to be determined include: total puff volume, mean puff volume, mean puff duration, mean inter-puff interval, mean maximum flow rate, and number of puffs.

At the conclusion of the second topography session, participants will practice the targeted puff volume smoking required of the following behavioral economic sessions. In contrast to the topography sessions, the behavioral economic sessions will require participants to achieve a target puff volume (70 ml) when they choose to self-administer cigarette puffs. This is because it is necessary to standardize puffs to ensure a constant reinforcer size across conditions. Product appeal will be assessed for both packages during these sessions.

Behavioral economics sessions (Sessions 3-9): In general, methods are modeled closely after those currently in place for research being conducted investigating reduced-nicotine

Date: February 18, 2023

Principal Investigator: [name].

Application Number: IRB00264306

NCT04595279

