cigarettes in our laboratory (IRB00107178). In 4 sessions, a demand curve will be generated for greenwashed cigarettes while control cigarettes will be available at a fixed price throughout. Specifically, in one session, both types of cigarettes will be concurrently available for the same fixed, low behavioral price (10 plunger pulls for a bout of 3 cigarette puffs). In the other 3 sessions, the control cigarettes will be available for 10 pulls, while the greenwashed cigarettes will be concurrently available for 100, 1000, or 10000 pulls (varying across the 3 sessions). This models the realistic situations in which greenwashed cigarettes are available at higher prices than other cigarettes. Then in another 3 sessions which provide an important comparison condition, we will assess the opposite situation, in which price for control cigarettes is 100, 1000, or 10000 pulls across sessions (the session in which both are available for 10 pulls will have already been conducted), and greenwashed cigarettes are available at a fixed price of 10 pulls throughout. The order of the 7 behavioral sessions (with different price combinations) will be randomized for each participant.

During sessions, after confirming the CO breath requirement, the participant will take 1 puff of each type of cigarette. A 3 hour self-administration session will start 30 minutes after the initial puffs. Initial puffs will standardize the time since last smoking across all participants and sessions. Participants will complete each session in 1 of 4 existing identical ventilated smoking rooms, each equipped with a computer connected to a response console used to collect data. The console will have two Lindsley-type response plungers (custom modeled after Gerbrands No. G6310, Ralph Gerbrands Co., Arlington, MA, USA) horizontally spaced equidistantly along the front of the console. A force of 20 N will be required to operate the plunger and register a response. Depending on the response requirement of the session, a certain number of plunger pulls will result in controlled self-administration of cigarette puffs (described in more detail in puffing procedure subsection below). Either the left or right side plunger will be randomly associated across participants with either the greenwashed or control cigarettes. We will supply all cigarettes.

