Using data from an ongoing operant demand study in our lab evaluating the substitutability of reduced-nicotine content cigarettes for full-nicotine cigarettes (grant R01DA042527), elasticity (α) of reduced-nicotine cigarettes was significantly greater than that of full-nicotine cigarettes (Cohen's $d = 1.33$). Although these analyses were limited to single-item demand (i.e. cigarettes not concurrently available), the same underlying principles are applicable to the current analysis. Assuming an effect size half as large ($d=.67$), a sample size of $N = 20$ would provide power $\geq 80\%$ (two-tailed; $\alpha=.05$) to detect a main effect of greenwashing tactics on demand metrics. Our proposed sample size of $N = 35$ would provide between 97-98% power in the current analyses comparing demand metrics between the cigarette packaging types, assuming an effect size of $d=0.67$ or 0.70 , respectively. A previous study comparing smoking topography of water pipe tobacco with and without graphic warning labels demonstrated significantly reduced total puff volume in the water pipe with the graphic warning label relative to the unlabeled pipe ($d=0.49$) (Maziak et al., 2019). Using the effect size from Maziak et al. (2019), which is comparable to the current approach, a sample size of $N = 35$ would provide $\geq 80\%$ power (two-tailed; $\alpha=.05$). Because the published topography data represent the smallest encountered effect size among the outcomes, we are powering the study to address this effect, which will provide a sample size that is beyond sufficiently-powered to address the aforementioned demand outcomes.

Demand metrics (demand intensity, demand elasticity, cross-price elasticity) and topography measures (total puff volume, mean puff volume, mean puff duration, mean inter-puff interval, mean maximum flow rate, and total puff number) will be compared between control and greenwashed cigarettes using paired-samples *t*-tests. Power analyses were performed for all primary behavioral economic and topography variables. Because topography measures showed the smallest anticipated effect based on published data ($d = 0.49$), we have conservatively based our sample size on topography. Despite this conservative estimation, if non-significant trends are observed suggesting potential effects, the proposed research will provide excellent data for informing power for future studies.

- d. Early stopping rules.

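### Brand name and plunger side are assigned at random with no balancing stated and are left out of the paired t-tests; balanced allocation plus two model terms would be a cheap, minor improvement

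*Combined protocol and SAP*

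**What the plan says.** All references are to the combined protocol and SAP.

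- **Brand name** (Section 4a, Greenwashing Manipulations): "To avoid a brand x greenwashing confound, the brand that is advertised with greenwashing materials will randomly vary across participants".
- **Plunger side** (Section 4a, Behavioral economics sessions): "Either the left or right side plunger will be randomly associated across participants with either the greenwashed or control cigarettes". Side has no role in the topography sessions.
- **Topography order** (Section 4a, Topography sessions): "Order of the two sessions will be randomized and counterbalanced across participants".
- **Order of the choice sessions** (Section 4a, Behavioral economics sessions): "The order of the 7 behavioral sessions (with different price combinations) will be randomized for each participant".
- **Numbers** (General Procedures, in Section 4a): "We will recruit and consent up to 100 individuals to accrue 35 non-treatment seeking male and female dependent cigarette smokers to complete the study".
- **Analysis** (Section 7c): the demand metrics and topography measures "will be compared between control and greenwashed cigarettes using paired-samples *t*-tests". No brand or side term is mentioned.

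For brand and side, the protocol gives no block size, target split or rule for replacing dropouts.

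**The concern.** Each participant has one pairing of brand name with condition throughout. The wording on side reads the same way: it is assigned across participants, and no switching between sessions is described. Pairing within a person therefore does not cancel a liking for one invented name or one plunger. That preference enters the person's greenwashed-minus-control difference in full, and only the allocation across participants can offset it.

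The primary outcomes come from choice between two concurrently available products, where name and side preferences could plausibly act. The protocol uses the stronger word, counterbalanced, for topography order but not for these two factors. In a sample of 35, an uneven split is quite likely. An average preference would then move the one estimate the study obtains, and an analysis that ignores the factors cannot correct for it.

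**Working it through.** **1. The plan's own power figures.** Paired t-test, noncentral t with n − 1 df and noncentrality d√n, two-sided α = 0.05:

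- n = 20, d = 0.67: 81.1% (stated: at least 80%)
- n = 35, d = 0.67 and 0.70: 97.1% and 98.0% (stated: "would provide between 97-98% power in the current analyses comparing demand metrics between the cigarette packaging types")
- n = 35, d = 0.49: 80.4% (stated: at least 80%)

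All reproduce. The sample size rests on d = 0.49, a topography effect.

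**2. Chance of imbalance.** Simple randomisation is assumed, Binomial(35, 0.5), two-sided:

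- 22:13 or worse: 0.175
- 23:12 or worse: 0.090
- 18:17, the best possible: 0.264
- at least one of brand and side at 22:13 or worse: 1 − (1 − 0.1755)² = 0.32

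**3. Model.** D = τ + b·s + c·q + e, where D is a participant's paired difference, s and q are ±1 codes for brand assignment and side, and e has SD 1. The quantities b and c are the average preferences shared across participants. They are not in the documents and are assumed at 0.2, 0.3 and 0.5.

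**4. Shift for a given split.** Shift = b × (22 − 13)/35 = 0.257b, which is 0.05 at b = 0.2 and 0.13 at b = 0.5. At 23:12 it is 0.314b, and at 18:17 it is 0.029b.

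**5. Type I error of the planned t-test (simulation).**

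- Averaged over simple randomisation: about 5% at every b = c tried.
- Given a 22:13 brand split: about 5.5%, 6.2% and 8% at b = 0.2, 0.3 and 0.5.
- Given a 23:12 brand split: about 6.0%, 7.3% and 10.4%.

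**6. Balancing and adjustment (simulation, n = 35).** Power is for d = 0.49 standardised by the SD of the differences as analysed, including preference variance. Each cell gives type I error / power.

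| b = c | Simple, no terms (assumed plan) | Balanced, no terms | Simple, both terms | Balanced, both terms |
|---|---|---|---|---|
| 0 | 5% / 81% | 5% / 81% | 5% / 78% | 5% / 80% |
| 0.2 | 5% / 80% | 4.1% / 81% | 5% / 81% | 5% / 83% |
| 0.3 | 5% / 81% | 3.4% / 82% | 5% / 84% | 5% / 86% |
| 0.5 | 5% / 80% | 1.6% / 84% | 5% / 92% | 5% / 93% |

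Check of the last column: removing both factors raises the effective d to 0.49 × √(1 + 2b²) = 0.509, 0.532 and 0.600. On 32 df this gives 83%, 86% and 93%.

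Topography has no side factor, so there the effective d is 0.49 × √(1 + b²) = 0.500, 0.512 and 0.548. On 33 df this gives about 82%, 84% and 88%.

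**7. After dropout.** The root-mean-square shift under simple randomisation is b/√35 = 0.169b. If 35 completers are a random subset of a balanced 40, 50 or 100, it is 0.061b, 0.094b or 0.137b.

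**The case against.** Four counter-arguments deserve weight.

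- **The confound.** A reader might infer that the brand confound remains despite the protocol's statement that it is avoided. The documents do not support that. Assignment at random for each participant removes the systematic confound, the estimate is unbiased over randomisations, and the t-test already counts the extra variance. Inflation exists only given an uneven split. The protocol also makes no claim about avoiding a side confound. This argument stands in full.
- **The power.** A reader might infer that power falls from 80% to 71%. That needs a preference of 0.5 SD and a planning d of 0.49 that excludes preference variance: 0.49/√1.25 = 0.438, power 71%. Section 7c does not say that d excludes it, and 0.49 is a secondary topography effect. On the same premise the demand effect becomes 0.67/√1.25 = 0.60, with power still about 93%. Adjustment is best seen as a possible gain, not as repair of a shortfall.
- **The size of the preference.** Both brands are novel, the cigarettes are identical and the packs are similar, so a shared preference may be small. Balancing and model terms remove only the shared part; individual likings stay in the differences. This also stands.
- **The wording.** Random variation does not exclude a blocked list. The supportable statement is that balancing is not specified.

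None of these removes the case for a better allocation and analysis that costs almost nothing.

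**Conclusion.** The point holds as a minor one. Balancing of brand name and plunger side is not specified, and the analysis ignores both factors. The design remains valid on average. What is at stake is the particular split obtained and some precision.

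The imbalance probabilities assume simple randomisation. The shift of 0.05 to 0.13 SD and the type I error of about 5.5% to 8% are conditional on a 22:13 split and on an assumed shared preference of 0.2 to 0.5 residual SD. The gain from about 80% to 83–93% power at d = 0.49 assumes that both factors act at that size. For topography, where only brand acts, the gain is to about 82–88%. If neither preference exists, there is nothing to gain and almost nothing to lose.

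**What to change.** 1. In Section 4a, state that brand name (A or B greenwashed) and plunger side (left or right) are allocated in permuted blocks together with topography order, which gives 2 × 2 × 2 = 8 combinations.
2. Replace a participant who drops out with one allocated to the same combination.
3. In Section 7c, analyse the paired differences in a linear model whose intercept is the greenwashing effect. Include a centred ± term for brand assignment in all outcomes and one for side in the choice-session outcomes.

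Steps 1 and 3 belong together: balancing without the terms makes the planned t-test conservative (type I error down to about 1.6% at 0.5 SD). If allocation has already been done, the terms alone still help, at a cost of about 2 points of power if neither factor matters.

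The cost is a prepared allocation list and at most two degrees of freedom, with no added sessions; the target of 35 completers is unchanged. Imbalance is reduced, not eliminated, because 35 is odd and not a multiple of 8, and because dropout can disturb the cells.

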The proposed double-blind laboratory study in 35 non-treatment seeking dependent smokers will determine the test the effect of greenwashing on behavioral economic self-administration and smoking topography. A within-subjects design will compare self-administration choice and smoking topography between two “brands” that in reality will be identical cigarettes with ads/labels that include vs. lack greenwashed tactics. Behavioral economic sessions will determine self-administration under concurrent availability of the two brands at various behavioral prices. Topography sessions will test ad-lib self-administration for each brand. Together, these sessions encompass the two primary ways advertising could affect smoking behavior (the amount smoked, and how one smokes). We hypothesize that greenwashed cigarettes will (a) show greater self-administration than non-greenwashed cigarettes when available at equivalent prices, (b) show reduced sensitivity to price compared to non-greenwashed cigarettes, and (c) will be self-administered more than non-greenwashed cigarettes even when their price is higher. We also hypothesize that in topography sessions greenwashed cigarettes will show: greater (a) total puff volume, (b) mean puff volume, (c) mean

Date: February 18, 2023

Principal Investigator: [name].

Application Number: IRB00264306

NCT04595279

puff duration, (d) mean maximum flow rate, (e) number of puffs; and lesser (f) mean inter-puff interval.

3. Background (briefly describe pre-clinical and clinical data, current experience with procedures, drug or device, and any other relevant information to justify the research)

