Greenwashing is an increasingly common strategy deployed by the tobacco industry to portray products as less harmful. Greenwashing involves portraying a product or brand as eco-friendly and/or natural (Laufer, 2003). Ours and others’ work has found this is accomplished through a variety of lexical and graphical tactics (Epperson et al., 2017; 2018). Lexical tactics include (a) Textual descriptors (e.g., additive-free, natural, organic, pure) and (b) textual references (e.g., claims about sustainable farming, lack of pesticides, limited ingredients (e.g., “Tobacco & Water”), supplemental environmental activities (e.g., planting trees). Graphical tactics include the use of (a) specific icons (e.g., leaves, flowers, seeds, recycling symbols) and (b) broader settings and background imagery (e.g., farms, forests, wood or natural background). Studies across multiple domains of consumer products, including tobacco, demonstrate that greenwashed products are seen as healthier than products that are not marketed using greenwashed tactics (Byron et al., 2015; Lazzarini et al., 2016; O’Connor et al., 2017).

Behavioral economics, which bridges analysis from microeconomics with the methods and subject matter of behavioral science, examines how behavior is maintained by reinforcers under systems of constraint (Hursh, 1980, 1984). Demand analysis has been widely applied to human and animal drug reinforcement (Hursh et al., 2015; Johnson et al., 2004). Demand refers to the amount of reinforcer (e.g., cigarettes) consumed. Demand at various prices can be used to construct a demand curve, which can be quantified with specific metrics. Demand intensity is the person’s preferred level of consumption of that reinforcer when it is virtually free (at a trivial price). Demand elasticity refers to the sensitivity of reinforcer consumption in response to

Date: February 18, 2023

Principal Investigator: [name].

Application Number: IRB00264306

NCT04595279

changes in price (monetary price or behavioral price, i.e., how much effort is required to obtain the reinforcer).

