A difference in any behavioral economic demand metric would be meaningful for the cigarette market, and traditional reinforcement measures do not examine all reinforcement aspects. For example, greater demand intensity for greenwashed compared to non-greenwashed cigarettes would indicate that greenwashing would increase cigarette consumption at the lower end of price ranges. Greater demand elasticity for greenwashed cigarettes compared to non-greenwashed cigarettes would indicate that greenwashing would increase cigarette consumption at higher prices in the commercial market, even if greenwashing had little or no effect at lower prices. Using progressive ratio breakpoint (a traditional reinforcement measure that corresponds to demand elasticity) would allow the study to miss meaningful differences in demand intensity. Using discrete choice (a traditional measure which typically uses a low price for both alternatives and is therefore analogous to demand intensity) would allow the study to miss difference in demand elasticity. Moreover, by examining reinforcer interactions (cross-price elasticity), demand analyses can inform the degree to which smokers would pay more for greenwashed cigarettes even if non-greenwashed cigarettes were available at a lower price. Therefore, the primary aims of the proposed study are to test the effect of greenwashing on behavioral economic self-administration measures. Additional topography measures will be conducted to determine smoking topography during ad-lib self-administration. Together, these sessions encompass the two primary ways advertising could affect smoking behavior (the amount smoked, and how one smokes).

4. Study Procedures

- a. Study design, including the sequence and timing of study procedures (distinguish research procedures from those that are part of routine care).

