Demand Metrics: Reinforcement will be assessed by the 2 essential demand metrics: demand intensity and demand elasticity; which are calculated with nonlinear regression using the exponential demand equation (Hursh & Silberberg, 2008). Auxiliary metrics (Pmax, Omax, breakpoint) will also be examined, although these are derivative of the essential metrics. Demand elasticity and demand intensity will be calculated for each cigarette type (greenwashed or control) as it escalates in price and the alternative cigarette price remains fixed. Cross-price elasticity will be calculated to quantify the effect of increasing greenwashed cigarette work requirements on control cigarette consumption, and vice-versa. These measures will indicate how greenwashing perceptions may increase smoking. Greater demand intensity for greenwashed cigarettes compared to nongreenwashed cigarettes would indicate that greenwashing would increase cigarette consumption even at the lower end of commercial price ranges. Greater demand elasticity for greenwashed cigarettes compared to nongreenwashed cigarettes would indicate that greenwashing would increase cigarette consumption at higher prices in the commercial market, even if greenwashing had little or no effect at lower prices. By examining reinforcer interactions (cross-price elasticity), demand analyses can inform the degree to which smokers would pay more for greenwashed cigarettes even if non-greenwashed cigarettes were available at a lower price.

- b. Secondary outcome variables.

Smoking Topography: We will collect six measures of smoking topography: total puff volume, mean puff volume, mean puff duration, mean inter-puff interval, mean maximum flow rate, and number of puffs. These data will be collected by ad lib smoking using our existing custom smoking topography system currently in use in our laboratory (IRB00107178). Our current research uses this topography system to help participants achieve a target volume per puff, but is already fully functional in its ability to measure topography of ad lib smoking. These measures will indicate the effect of greenwashing on how people smoke cigarettes in more damaging ways, for example, by smoking more deeply (greater puff volume), faster (greater maximum flow rate, lower inter-puff interval), or with increased time in lungs (greater puff duration).

- c. Statistical plan including sample size justification and interim data analysis.

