Analysis of Demand Curves: A paired-samples *t*-test will examine each demand metric, with data transformations of each demand metric if non-normally distributed (square root transform of Q0 and natural-log transform of α). We expect different demand profiles (greater demand intensity, and lower elasticity of demand) when cigarettes are greenwashed compared to control cigarettes.

Analysis of Cross-Price Elasticity: To calculate cross price elasticity of cigarettes, any instances of zero self administrations within a block will be coded as 0.5 because the logarithm

Date: February 18, 2023

Principal Investigator: [name].

Application Number: IRB00264306

NCT04595279

of zero is undefined. Then, a linear regression will be performed on the log10 of consumption means vs. the log10 of unit prices. The resulting slope of this regression line will be the cross-price elasticity.

Analysis of Smoking Topography: Paired-samples *t*-tests will be used to compare measures of smoking topography between the greenwashed and control cigarettes.

Statistical power:

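### Section 7 names no test of observed consumption in the equal-price (10/10) session for hypothesis (a); the nearest planned metric, fitted Q0, extrapolates below the lowest price and absorbs price response

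*Combined protocol and SAP*

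**What the plan says.** - Section 2 (Objectives), hypothesis (a): greenwashed cigarettes will "show greater self-administration than non-greenwashed cigarettes when available at equivalent prices".
- Section 3 (Background) defines demand intensity as the "preferred level of consumption of that reinforcer when it is virtually free (at a trivial price"). It describes discrete choice as a measure that "typically uses a low price for both alternatives and is therefore analogous to demand intensity".
- Section 4a (Behavioral economics sessions) has seven sessions. In one, the two brands are "concurrently available for the same fixed, low behavioral price (10 plunger pulls for a bout of 3 cigarette puffs"). In the other six, one brand stays at 10 pulls and the other costs 100, 1000 or 10000. Each brand's curve thus has four points, and only the first comes from an equal-price session.
- Section 7a takes the primary metrics from a fitted curve: "demand intensity and demand elasticity; which are calculated with nonlinear regression using the exponential demand equation".
- Section 7c: "A paired-samples *t*-test will examine each demand metric", with a "square root transform of Q0 and natural-log transform of α" if the data are not normal. Intensity therefore enters the test as the fitted Q0.
- Section 7 does not give k, the scale of the fit, or the handling of zeros in the demand fit. The rule coding zero as 0.5 is stated only for cross-price elasticity.

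**The concern.** The design observes the quantity in hypothesis (a) directly, within person, in the 10/10 session, yet no listed analysis uses that observation on its own. Intensity is the only listed metric close to it, and Q0 is consumption at price zero. No price lies below 10 pulls and none between 10 and 100, so the step from Q(10) to Q0 is governed by how fast consumption falls at higher prices, all of them seen in unequal-price sessions.

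This matters because hypothesis (b) expects the control brand to be the more price-sensitive. If it is, Q0 is raised more for control than for greenwashed cigarettes, which works against hypothesis (a). Steep falls are plausible: both brands are the same cigarette, and the alternative stays at 10 pulls while the other costs 10 to 1000 times as much. Section 7a presents effects at low and at higher prices as separable, but the fitted Q0 does not guarantee that.

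**Working it through.** **1. The plan's own power figures.** Exact paired t-test power (two-sided 0.05, df = n - 1, noncentrality d√n) gives:
- n = 20, d = 0.67: 81.1%
- n = 35, d = 0.67: 97.1%
- n = 35, d = 0.70: 98.0%
- n = 35, d = 0.49: 80.4%

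All agree with section 7c. The demand effect size is half of an observed d of 1.33 for elasticity (α), so these figures say nothing specific about Q0.

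**2. Q0 relative to 10-pull consumption.** The plan cites the exponential equation without writing it out. The standard form is assumed here:

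log10 Q(P) = log10 Q0 + k(exp(-α·Q0·P) - 1).

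Put x = exp(-10·α·Q0). Then
- log10[Q(10)/Q(100)] = k(x - x^10)
- Q0/Q(10) = 10^(k(1 - x))

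With k = 2:

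| Fall from 10 to 100 pulls | x | Q0/Q(10) |
|---|---|---|
| 2-fold | 0.9817 | 1.09 |
| 8-fold | 0.9287 | 1.39 |
| 16-fold | 0.8797 | 1.74 |

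For the 8-fold fall, k = 1.5 gives x = 0.8797 and a ratio of 1.52; k = 3 gives x = 0.959 and 1.33.

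If greenwashed consumption falls 2-fold and control 8-fold, Q0 favours control whenever the observed greenwashed advantage at 10 pulls is below 1.39/1.09, that is, below about 28%.

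**3. Reversal without any misfit.** With k = 2, take greenwashed Q0 = 12, α = 0.00002 and control Q0 = 14, α = 0.0005. Consumption at 10 pulls is 11.87 v 10.25, yet Q0 ranks 12 below 14. The shallow greenwashed curve has Q0/Q(10) = 12/11.87 = 1.01.

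**4. Fits to illustrative data.** Least-squares Q0, greenwashed v control (bouts at 10/100/1000/10000 pulls):

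| Bouts | Scale of fit | k = 1.5 | k = 2 | k = 3 |
|---|---|---|---|---|
| 12/10/6/0.5 v 11/4/0.5/0.5 | log | 11.5 v 14.7 | 10.9 v 35 | 10.5 v about 1000 |
| same | consumption | 11.5 v 12.6 | 11.5 v 12.5 | 11.5 v 12.4 |

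The order at 10 pulls (12 v 11) is reversed throughout. A 3-hour session with 180 seconds per bout holds at most 10800/180 = 60 bouts, so a Q0 near 1000 is impossible. By contrast, 12/11/6/0.5 v 10/6/2/0.5 keeps the right order (for example 12.1 v 11.0 on the log scale at k = 1.5).

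**5. Simulation.** 600 trials of N = 35 per scenario; within- and between-person log-SD 0.35; paired t-test on √Q0 against a paired t-test on 10/10 bouts. Mean bouts are assumptions. Log fits code zeros as 0.5. Entries are the percentage significant; right means favouring greenwashed, wrong means favouring control.

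| Mean bouts, greenwashed v control | Direct, right | Q0 log fit, k = 1.5/2/3: right | Q0 log fit: wrong | Q0 consumption-scale fit, k = 2: right / wrong |
|---|---|---|---|---|
| 12/9/4/0.2 v 10/4/1/0.2 | 49-51 | 0/0/0 | 55/99/100 | 12 / 0 |
| 12/7.2/2.4/0.2 v 10/6/2/0.2 | 46-50 | 19/8/5 | 2 or less | 4 / 1 |
| 11/9/4/0.2 v 11/4/1/0.2 (equal at 10) | 1-3 | 0/0/0 | 92/100/100 | 2 / 5 |

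Further consumption-scale simulations under other assumptions gave Q0 power of 0-28% against 27-96% for the direct test where a 10/10 difference existed. One equal-at-10 scenario gave 21% significant results in the wrong direction.

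**The case against.** The case for leaving the plan as it is has real force on four points.

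- **The link to Q0 is an inference.** A reader might infer that the plan designates Q0 as the test of hypothesis (a). It does not: section 2 does not mention intensity when it states (a), and section 7a relates intensity to the low end of commercial prices. What stands is that section 7 names no test matched to (a) and that Q0 is the closest candidate.
- **Sign reversal is not general.** A reader might infer that the planned analysis will point the wrong way. The documents do not support that, because the result turns on choices they leave open. The pattern 8/3/1/0 gives a Q0 of 18 (k = 1.5) or 114 (k = 2) on the log scale with zeros coded 0.5, but at k = 2 only 9.0 on the consumption scale and 5.7 on the log scale with the zero omitted. The 0.5 rule is not stated for this fit. Some reversals are also fragile. On the consumption scale at k = 2, 9/3/1/0 v 7/0/0/0 gives 10.4 v 16.3, but a single control bout at 100 pulls (7/1/0/0) gives 9.4 and restores the order.
- **Power comparisons rest on invented consumption.** In another simulation (mean 12 bouts, a 62/38 split at equal prices, the same proportional price response), Q0 power ran from 5 to 60%, 19-21% in the central case, against about 55-67% for the direct test. The ranges overlap. The loss is one of efficiency under assumptions and does not make the Q0 test invalid.
- **Q0 is a legitimate curve summary.** Section 3 argues for demand metrics on purpose, and α is tested beside Q0. Reducing Q0 to a purely descriptive output would go further than the problem requires.

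None of this supplies a test of observed equal-price consumption.

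**Conclusion.** The concern holds in a bounded form and should be fixed. Hypothesis (a) has no named test in the one session that observes it, and the nearest metric mixes price response into intensity by construction. Under the standard equation at k = 2, the inflation over 10-pull consumption is 9% for a 2-fold fall and 74% for a 16-fold fall. A steeper control curve can cancel or outweigh a modest equal-price advantage. In the assumed scenarios Q0 usually loses much of the power of the direct comparison.

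How often the sign would reverse cannot be determined from the documents. In the simulations with a steeper control curve, the log fit with zeros as 0.5 gave significant wrong-direction results in 55-100% of trials. The consumption-scale fit in the tabulated scenarios gave 0-5%. The conclusion assumes the standard form of the equation, a common k for both brands, and consumption profiles that the plan does not provide.

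**What to change.** In sections 7a and 7c:

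1. Prespecify, as the test of hypothesis (a), the paired comparison of greenwashed and control bouts in the 10/10 session, or the greenwashed share of bouts against 50%. Choose one and name it.
2. Keep fitted Q0 as a supporting demand metric, tested and reported as such.
3. State the form of the equation, the value of k (or how it is set, and that it is common to both brands), the scale on which the curve is fitted, and the handling of zeros in the demand fit.

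The cost is a few sentences, with no new sessions, participants or data. There are two small downsides: the test of (a) then rests on one session per person, and it is not the Q0 customarily reported in demand studies, although Q0 remains available beside it.
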